An intervention to Promote Positive Peer Relationships and Reduce Prejudice and Bias in Childhood, July 16, 2025

Study Protocol

The objectives of this project was to test the beneficial impacts of an intervention, *Developing Inclusive Youth (DIY)*, for outcome measures reflecting increasing school belonging, classroom support, and intergroup attitudes (reducing stereotypes and biases) relative to a counterfactual (the business-as-usual control condition). A multi-site within-school randomized control trial (RCT) intervention design was employed to promote positive intergroup relationships and to reduce prejudice in childhood. The program was implemented under routine conditions in authentic education settings (grades 3, 4, and 5) which in this case was a large ethnically diverse public school district in the Maryland suburbs of Washington, D.C. The program had two components to it: 1) individualized viewing of a web-based curriculum tool depicting peer inclusion and exclusion scenarios; and 2) a group experience in which the teacher led a classroom discussion session that immediately followed students' use of the tool.

The web-based curriculum tool developed by the P.I.'s research team was an opportunity to view depictions of peer groups discussing everyday situations involving inclusion and exclusion, with a focus on multiple target groups: race and ethnicity (African-American, Latino/a, Arab-American, Asian-American, European-American), wealth status (high/low), and immigrant-status (non-native student). These categories were selected based on the developmental science literature that has demonstrated that these target groups experience victimization and social exclusion in peer contexts during the elementary school years (Brown, 2017; Rutland & Killen, 2015). Other significant target groups that have experienced exclusion and discrimination, such as physical disability or gender non-conforming, were not included in the program due to the constraints of an 8-week curriculum program (with a limit of 8 target groups). However, by providing students with a variety of excluded groups it was expected that children would generalize the lessons learned to groups not covered explicitly by the program.

The goals of the program were to provide children with the experiences of viewing both inclusive and exclusive decisions by characters similar to their peers. Providing a range of target groups increases the chance that one of the groups would reflect children's own identity in order to provide an affiliative experience with an excluded child..

The screenshot shows a user interface for the DIY tool. At the top, there is a dark header bar with a circular logo on the left, the text 'Logged in as: Educator' in the center, and a 'Logout' button on the right. Below the header is a yellow section titled 'Let's Begin!' in bold black text. Underneath the title is the sub-instruction 'Click on today's story' in a smaller, regular black font. The main content area is a grid of eight colored boxes, each representing a scenario: 1. Recess (blue box, showing children playing with a ball and jump rope), 2. Science (yellow box, showing children at a lab table with test tubes), 3. Park (purple box, showing children on a tire swing), 4. Bowling (orange box, showing children with bowling balls), 5. Arcade (red box, showing children in bumper cars), 6. Dance (light blue box, showing children dancing), 7. Party (yellow box, showing children with balloons), and 8. Movie (purple box, showing children sitting in bean bags). Each box has a small number and the scenario name at the top.

Figure 1. Portal for beginning the DIY tool, revealing the 8 scenarios that are entered, one per week for 8 weeks: Recess, Science, Park, Bowling, Arcade, Dance, Party, and Movie. Illustrations © [name].

The content of the DIY web-based interactive tool and teacher training manual drew on well-established theoretical and empirical lines of research on prejudice and social exclusion in childhood (Abrams & Killen, 2014; Brown, 2017; Cameron & Rutland, 2006; Killen, Lee-Kim, McGlothlin, & Stangor, 2002; Levy, et al., 2016; Rutland et al., 2024; Turner & Cameron, 2019).

Children progressed through 8 scenarios, one per week, all of which are available at the DIY portal (see Figure 1). The interactive design of the tool allows children to watch simulated peer interactions that involve social exclusion and then children are asked to make decisions, form judgments, and observe the outcomes of their own decision-making (these responses are recorded in the tool and produced as a .CSV file for statistical analyses).

After each child has had an opportunity in the classroom to individually complete the scenario of the week using the web-based curriculum tool, teachers led a guided discussion regarding the choices and decisions presented in the tool. Teachers lead this discussion without knowledge of, or reference to, student's own individual decisions. However, teachers were provided with a sequence of questions designed to foster discussion. Teachers asked students to discuss their own experiences relevant to the scenario. The issues surrounding each scenario are about social inclusion and exclusion, stereotypic expectations, biases, peer relationships, friendships, shared interests, and common goals. Thus, the scenarios depicted in the web-based curriculum tool provide the basis for substantive teacher-led face-to-face classroom discussions.

Overall, the intervention program created two types of intergroup contact, indirect and direct (Levy, et al., 2016; Tropp & Prenovost, 2008; Turner & Cameron, 2019). The *indirect contact* in the intervention program occurred with the use of animated intergroup scenarios in the web-based curriculum tool (which children viewed on their laptops in the classroom). Children watched peer exchanges in which children like themselves become friends with those from different backgrounds, and they learn that these peers have common goals and shared interests. The *direct contact* occurred in the program when children discussed their views of the peer scenarios in class with children from different backgrounds and when these discussions occurred among peers. The use of both direct and indirect intergroup contact as well as eight different target groups enabled the project to test a theory of change.

Thus, there were three central aims of this proposed project:

Aim #1. The first aim of the proposed project was to chart the grade-related, gender-related and ethnic-related differences regarding socioemotional well-being and prejudicial attitudes and behaviors of U.S. 3rd, 4th and 5th graders through the use of baseline data collected pre-intervention.

Aim #2: The second aim of this proposed project was to test whether the intervention (class-based curriculum tool with classroom discussion, *Developing Inclusive Youth (DIY)*) was effective in *enhancing sense of school belonging and well-being* for children, relative to children in the business as usual (control) condition.

Aim #3: The third aim of the proposed project was to test whether a class-based intervention (class-based curriculum tool with classroom discussion, *Developing Inclusive Youth (DIY)*) was effective in *reducing prejudicial attitudes and behaviors*, relative to children in the business as usual (control) condition.

Method

Settings and Participants. Participants were 3rd, 4th, and 5th grade students (8 – 11 years of age), representing a range of racial and ethnic groups (European-American, African-American, Latino/a, Asian-American, and Multiracial), $N = 885$. The study was implemented in a large public school district in the Mid-Atlantic region of the U.S.

Procedure and Scenarios. The animated and narrated computer based tool was accessed through a password-protected internet link housed at the University of Maryland under the supervision of the P.I. Unique login IDs are distributed to children whose parents have given consent for participation. Participating students had a laminated card with the name and login ID

on it which was distributed to them at the beginning of each session (and retrieved at the end of each session). And these login IDs allowed for the tracking of responses over the course of the 10-week program.

Table 1. Design of the Pre-test, Intervention Program, BAU Group, and Post-test

Design	Screening 1	Block A	Screening 2	Block B	Screening 3
	Week 1	Weeks 2- 9	Week 10	Weeks 11-17	Week 18
Intervention Program	Pretest Administered	Program	Posttest I Administered	BAU	Posttest II Administered (follow-up)
Control Group (Business as Usual)	Pretest Administered	BAU	Posttest I Administered	BAU	Posttest II Administered (follow-up)

The **control group** was Business-As-Usual. The **intervention program** included children using the web-based curriculum tool for 15 minutes in the classroom followed by a 30-minute discussion period once a week for eight weeks. During each intervention session children would respond to one of the eight scenarios (with a new target group each week). This was a 10-week program.

All participating students respond to four types of prompts in the web-based curriculum tool to keep students engaged as they viewed the scenarios: *Feeling Attributions* (for each character), *Evaluations*, *Reasons*, and *Decisions*. The specific questions and response options are the following: 1) *Feeling attributions*: “How good or bad do you think X feels when [exclusion happens]?” [options are from Very good to Very bad with smiley to frowny faces (1 – 6 scale); 2) *Evaluations*: “Is it okay for X to [exclude Y]?” [options are Okay or Not Okay]; 3) *Reasons*: “You’re chosen X, why is that? Choose the reason that you think is most important [options are one of four reasons, moral, group functioning, stereotypes, personal choice]”; 4) Decision to include or exclude: “What do you think? Should X and Y [exclude or include]” [options are Exclude or Include]. For example, for the Recess scenario, the Decision options are “Keep playing with just the two of them” or “Invite Sophie to join” which reflect Exclude or Include, respectively.

After completing the 15-minute scenario, the teacher generated discussion in the classroom for 30 minutes using the *Teacher Manual*. Teachers ask the students to sit in a circle on the floor in the front of the classroom for the discussion immediately following the students’ completion of the tool. Teachers use a picture card depicting the characters in the story with their name on it to facilitate the discussion. Following the teachers guidelines, teachers covered four areas for discussion, which included soliciting the students’ interpretations of the scenario, their selections for the characters’ emotions and perspectives, their evaluations of the characters’ choices, and connections between the scenarios and the students’ daily experiences. The teacher wrapped up the discussion with a summary of the main message of the week for the scenario.

The 8 target groups were as follows: 1) new kid at school; 2) gender; 3) Latino peer; 4) immigrant status; 5) high/low wealth status; 6) African-American peer; 7) European-American peer at an Asian party; and 8) Arab peer (more details about the scenarios are provided below). These contexts and groups were identified for the program based on research

on social inclusion and exclusion and extensive pilot testing over the past 3 years (Brown, 2017; Killen & Rutland, 2011; Rivas-Drake, et al., 2014; Ruck, Peterson-Badali, & Freeman, 2016). It is important to note the goal of this program is not to fully address any one group but to discuss exclusion more generally as research has demonstrated that reducing biases and prejudice about one group generalizes to other biases about other groups (Rutland & Killen, 2015).

The first scenario “New Kid” depicted an exclusion context that was not associated with group membership identity. This started off the 8-week session with an exclusion experience that was not targeted at stereotypes associated with groups but with a general experience (being new) that most children can identify with. The scenarios were drawn from every-day school and home peer encounters and based on vignettes used in developmental science research (see Killen & Rutland, 2011). Each of the 7 subsequent scenarios depicted a dyad or a group discussing whether or not to exclude a target child from one of the groups identified: a science project assignment in class in which boys discuss not including a girl to join them, a discussion at the park around turn-taking on a tire swing in which boys discuss excluding a Latino boy from having a turn, a bowling outing in which girls discuss not including a girl who has an accent and is newly arrived to the country, low-wealth peers at an arcade who are hesitant to play with high wealth peers, a ballet club that is unsure about admitting a new girls who is African-American, an Asian birthday party in which boys discuss whether to invite a European-American boy who would be the only non-Asian at the party, and two boys, one Arab and one not discussing whether to watch a movie with Arabs portrayed as the “bad guys”. The scenarios in the web-based curriculum tool drew from an extensive database of peer exclusion scenarios reported by children from a wide range of backgrounds (Killen & Rutland, 2011).

American Disability Act (ADA) Compliance. The tool meets American Disability Act compliance because all information is presented visually (words on the screen) as well as through auditory means (voice-over) and meets 508 Compliance consistent with the University of Maryland guidelines.

An intervention to Promote Positive Peer Relationships and Reduce Prejudice and Bias in Childhood

Analysis Plan

16 July 2025

1. Hypotheses

- 1.1. We expected that compared to the control condition, participants in the treatment condition would:
 - 1.1.1. report higher **school belonging, peer support, and teacher support** at posttest.
 - 1.1.2. report lower levels of **personal experiences with exclusion** at posttest.
 - 1.1.3. report higher **contact with diverse peers** at posttest.
 - 1.1.4. report higher **desire to play with diverse peers** at posttest.
 - 1.1.5. more negatively **evaluate exclusion** at posttest.
 - 1.1.6. have higher **high-status occupation expectations** about marginalized groups (girls, Black peers, Latine peers) at posttest.
 - 1.1.7. make more positive **trait attributions** of diverse peers at posttest.
 - 1.1.8. have higher **expectations of inclusivity** of different peer groups at posttest.
 - 1.1.9. have more positive **math and science competency beliefs** about marginalized groups (girls, Black peers, Latine peers) at posttest.
- 1.2. We expected treatment effects to vary by participant race/ethnicity for school belonging, peer support, teacher support, personal experiences with exclusion, contact with peers of different race/ethnic groups, desire to play with peers of different race/ethnic groups, evaluations of exclusion of different race/ethnic groups, high status occupation expectations about marginalized racial groups, beliefs about the inclusivity of different race/ethnic groups, math and science competency beliefs about different race/ethnic groups, and trait attributions of different race/ethnic groups.
- 1.3. We expected treatment effects on the above listed outcome measures to vary by grade. Older children may exhibit greater change on these measures due to more awareness of group dynamics. However, a previous iteration of this program (conducted with a more racially homogeneous sample) found that compared to 5th graders, 3rd graders showed more change from pre to posttest.
- 1.4. Exploratory hypotheses: We tested for school effects due to differences in their racial composition. We also examined 2-way treatment interactions with school, race, and gender to determine whether the program was more effective for certain child demographic groups.

2. Measured variables

1. School belonging*
2. Peer support*
3. Teacher support*
4. Personal experiences with exclusion*
5. Reported contact
6. Desire to play
7. Evaluations of exclusion
8. High status occupation expectations
9. Positive trait attributions*
10. Expectations of inclusivity
11. Math and science competency beliefs

**Indicates mean composite variable*

Measures also included in analyses, depending on model selection:

- Participant race/ethnicity (parent report)
- Gender (parent report)
- Grade level (3, 4, 5)
- Pretest measure for the respective outcome model was included as a control in each model
- School

Analysis Procedure

We first examined ICCs for classroom level and school level to determine if multilevel modeling was needed and conducted model comparisons to determine if classroom, school, and sex should be included as fixed effects. We selected models for each outcome variable based on lowest AIC and BIC.

We also conducted exploratory factor analyses on reported contact measures, desire to play measures, and evaluations of exclusion to determine if creating composite measures was most appropriate for analysis.

For all models, we included school, classroom, and gender if model comparisons indicate, using the model with lowest AIC and BIC for a given outcome variable.

We conducted multiple regression linear regression for all **composite variables**, using the base model:

```
lm(posttest DV ~ pretest DV + treatment*grade + race-ethnicity)
```

For all individual items for **reported contact, desire to play, evaluations of exclusion, expectations of inclusivity, and math/science competency beliefs**, we conducted ordinal logistic regression using the base model:

```
polr(posttest DV ~ pretest DV + treatment*grade + race-ethnicity)
```

For **high status occupation expectations**, we examined outcome distributions to determine if it is appropriate to collapse response options by stimuli gender and/or race. We conducted multinomial logistic regression using the base model:

```
multinom(posttest DV ~ pretest DV + treatment*grade + race-ethnicity)
```

Exploratory Analyses

For the above models, we tested the model removing the grade*treatment interaction, if it is not significant, to isolate the treatment effect. We also tested interactions of treatment*grade and treatment*gender to determine if the treatment was more effective for certain demographic groups.

Inference criteria

We considered predictors significant at a *p*-value of .05. We used Bonferroni adjustment for multiple groups pairwise comparisons.

Data exclusion

Children who could not independently complete the survey and had no trained adult available to assist them complete the pre-test and/or post-test were excluded from the sample and the subsequent analyses.

Missing data (optional)

We conducted imputations using predictive mean matching to address missing values. We imputed 30 datasets using the “mice” package in R. Demographic variables (grade, classroom, condition, gender, and school) were included as predictors, while pretest scores, posttest scores, and race were included as both predictors and imputed values. All analyses were conducted on the 30 imputed datasets individually and the pooled results were reported.

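### Adjustment for classroom is left to an ICC check with no cut-off and an AIC/BIC rule with no tie-break; if classrooms were assigned, classroom and school should be in every treatment model.

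*SAP*

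**What the plan says.** The SAP, Analysis Procedure, sets two data-dependent steps. The first is an ICC check: "We first examined ICCs for classroom level and school level to determine if multilevel modeling was needed". No value is given at which multilevel modelling becomes necessary. In the second, the authors "conducted model comparisons to determine if classroom, school, and sex should be included as fixed effects". The rule is repeated for all models: "we included school, classroom, and gender if model comparisons indicate, using the model with lowest AIC and BIC". Nothing says which criterion prevails when AIC and BIC prefer different models.

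No base model has a classroom term, and no multilevel form is written:

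- composites: "lm(posttest DV ~ pretest DV + treatment*grade + race-ethnicity"
- ordinal items: "polr(posttest DV ~ pretest DV + treatment*grade + race-ethnicity"
- occupation expectations: "multinom(posttest DV ~ pretest DV + treatment*grade + race-ethnicity"

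SAP, Missing data, says that all analyses were run on each of 30 imputed data sets and pooled. It gives no rule for the case where model selection differs among them. It also lists classroom as an imputation predictor, so the identifier exists.

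On design, the Protocol's opening section says "A multi-site within-school randomized control trial (RCT) intervention design was employed". It does not say whether classrooms or children were assigned. The Protocol describes a weekly classroom session with the web tool followed by a teacher-led discussion.

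**The concern.** A weekly discussion led by the class teacher is hard to give to some children in a room and not to others, so classroom assignment within schools is the natural reading. In that case children in one classroom share both their assignment and any classroom-level influence on the outcome. A single-level model then treats 885 children as independent, and its standard errors for treatment (hypothesis 1.1) and treatment by grade (hypothesis 1.3) are too small.

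A preliminary check does not remove the problem. An ICC too small to trigger the check, or to overcome the BIC penalty, can still inflate the error rate when classes are large. The rate then depends on a cut-off or tie-break that the SAP does not state.

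The one form in which the SAP says classroom may enter is a fixed effect. If whole classrooms were assigned, classroom indicators determine the arm completely, so the treatment effect cannot be estimated beside them.

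**Working it through.** **Inputs from the documents.** 885 participants (Protocol, Settings and Participants); significance at .05 (SAP, Inference criteria), taken as two-sided. The documents give no number of classrooms, class size, ICC or sample-size calculation, so there is no stated figure to reproduce.

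**Assumptions.** Classrooms assigned; 36 classrooms; residual classroom ICC 0.02 to 0.05.

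**Step 1: classroom ignored.** Children per classroom m = 885/36 = 24.6. DEFF = 1 + (m - 1) x ICC, and actual size = 2{1 - Φ(1.96/√DEFF)}.

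- ICC 0.02: DEFF = 1 + 23.6 x 0.02 = 1.472; 1.96/1.213 = 1.616; size 10.6%.
- ICC 0.05: DEFF = 1 + 23.6 x 0.05 = 2.18; 1.96/1.476 = 1.328; size 18.4%.

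This is an upper bound, because the SAP does check.

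**Step 2: classroom kept only if the check triggers.** Trials were simulated with no treatment effect. A classroom random intercept was kept if AIC fell (likelihood-ratio statistic above 2), if BIC fell (above ln 885, about 6.8), or if the estimated ICC exceeded an assumed cut-off of 0.05. Type I error for treatment, nominal 5%:

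| Rule | No school differences, ICC 0.02 / 0.05 | Range when school differences are absent or removed by a school fixed effect |
|---|---|---|
| AIC | 7.2% / 5.6% | about 6-9% |
| BIC | 9.6% / 8.3% | about 8-12% |
| ICC cut-off 0.05 | 10.3% / 11.2% | about 10-12% |
| Classroom ignored | 10.6% / 18.4% (step 1) | about 11-19% |
| Classroom always modelled | about 5% | about 5% |

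Smaller classes lessen the harm. In a separate simulation without school differences, at ICC 0.02 / 0.05:

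- 44 classrooms of 20: AIC 6.5% / 5.3%, BIC 8.5% / 7.3%, cut-off 0.05 9.2% / 10.0%.
- 88 classrooms of 10: AIC 5.8% / 5.3%, BIC 6.8% / 7.1%, cut-off 0.05 6.8% / 7.2%.

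The missing tie-break matters: with 44 classrooms, AIC and BIC disagreed in 34% and 22% of trials.

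**Step 3: treatment by grade.** With 36 to 60 classrooms and ICC 0.02, the joint interaction test rejects in 7.4-9.3% of trials under AIC choice and 9.1-12.2% under BIC choice. With classroom always modelled it rejects in 4.3-5.2% over ICC 0.01 to 0.10.

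**Step 4: schools differ and no school term is fitted.** Assume a school variance of 0.02 to 0.05 of child-level variance, 36 classrooms and ICC 0.01 to 0.10. The always-modelled classroom intercept then rejects in only about 1-4% of trials, because school differences that within-school assignment balances are counted as classroom noise. At school variance 0.05 the rates are 1.8-2.6% with AIC, 2.6-3.3% with BIC and 2.7-4.2% with a 0.05 cut-off. At 0.02, BIC gives 4.0-6.6% and the 0.05 cut-off 4.1-7.8%.

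**Step 5: classroom as a fixed effect.** With 44 classrooms, the design matrix of intercept and classroom indicators has rank 44; adding the treatment column leaves it at 44. Treatment is aliased. Requiring both AIC and BIC to be lowest selects these indicators in at most 0.1% of trials, but AIC alone does so in 23-61% at ICC 0.05 (36 to 60 classrooms).

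**Step 6: children assigned within classrooms.** With classroom omitted and no clustering from group delivery, size is 4.1%, 3.7% and 2.6% at ICC 0.05, 0.10 and 0.20. There is no inflation.

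**The case against.** The strongest reply is that the plan does consider clustering, and that the premise and every ICC here are assumed. That largely stands.

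- A reader might infer that the trial was cluster-randomized and its tests are therefore invalid. The documents never name the unit, and step 6 shows no inflation under individual assignment without delivery-induced clustering.
- A reader might infer that clustering was ignored. The SAP names classroom as a candidate, so the 11-19% is a bound and does not describe the plan. The list headed "Measures also included in analyses, depending on model selection" includes school but not classroom; little hangs on that, since Analysis Procedure names classroom twice.
- Larger figures come from an assumed cut-off of 0.10, for example 12.8-18.3% for treatment at ICC 0.05 with 36 to 60 classrooms. The documents contain no such cut-off.
- If the ICC was computed before covariate adjustment, the check triggers more readily. With 0.05 extra between-class variance (assumed), a 0.05 cut-off gives 4.8-5.8% for treatment, so almost no harm.
- It is tempting to say that modelling classroom always holds 5% whatever the ICC. Step 4 refutes this when school is left out, and SAP hypothesis 1.4 itself anticipates school differences.

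Two counter-arguments fail. AIC selection is not harmless, since it reaches 9.3% for treatment by grade. And considering clustering is not the same as accounting for it, as step 2 shows.

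**Conclusion.** The concern holds in a conditional form and should be fixed. The SAP leaves adjustment for classroom to unstated thresholds, and the classroom fixed effect it offers cannot work if classrooms were assigned. Under classroom assignment, with the assumptions in step 2, the treatment test's error rate is somewhere from about 6% to 12%, depending on the rule used, against about 5% with classroom always modelled. If schools differ and no school term is fitted, the error can run the other way and cost power. The documents therefore do not support saying that the reported tests must be anti-conservative; they leave the direction and size of the error undetermined. Confidence is medium, because the unit of assignment, number of classrooms, ICC and school variance are all unstated.

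**What to change.** State the unit of assignment and the number of classrooms per arm. If classrooms were assigned:

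- Account for classroom in every treatment model, whatever the ICC, AIC or BIC. For composites, use a classroom random intercept with small-sample degrees of freedom (Satterthwaite or Kenward-Roger). For the ordinal and multinomial models, use classroom-clustered variance with a small-sample correction.
- Include school as a fixed effect in every model, to match within-school assignment.
- Remove classroom from the candidate fixed effects and limit AIC/BIC to child covariates such as gender.
- Use the same model form in all 30 imputed data sets, and report ICCs as description only.

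The small-sample correction matters. With corrected clustered variance, simulated ordinal tests ran at 4.0-5.5% for treatment and 4.9-6.4% for treatment by grade; uncorrected, 6.0-7.7% and 8.2-11.9%. The multinomial figures were 4.5-5.5% and 5.2-6.9% corrected, 7.2-9.0% and 11.1-18.2% uncorrected. So a small excess can remain for the interaction. Pooling over imputed data sets was not part of these checks.

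The cost is SAP wording and a re-run, with no new data. Without a school term, treatment standard errors from the random intercept were wider than single-level ones by about 3-5% at ICC 0, 13-21% at 0.02 and 30-47% at 0.05; above ICC 0, most of this is uncertainty that the single-level model hides. If the true classroom ICC is zero, the test is slightly conservative (about 4%). The school term also uses some classroom-level degrees of freedom.

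### If whole classes were assigned, entering classroom as a fixed effect makes the treatment and treatment-by-grade effects inestimable; the SAP allows this and specifies no alternative form

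*SAP*

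**What the plan says.** **Form of the classroom term.** The SAP (Analysis Procedure) reports that the analysts "conducted model comparisons to determine if classroom, school, and sex should be included as fixed effects". It then states: "For all models, we included school, classroom, and gender if model comparisons indicate, using the model with lowest AIC and BIC" for the outcome in question.

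**Base models.** All three are single-level: "lm(posttest DV ~ pretest DV + treatment*grade + race-ethnicity") for composites, "polr(posttest DV ~ pretest DV + treatment*grade + race-ethnicity") for individual ordinal items, and "multinom(posttest DV ~ pretest DV + treatment*grade + race-ethnicity") for high-status occupation expectations.

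**Multilevel option.** The same section opens with "We first examined ICCs for classroom level and school level to determine if multilevel modeling was needed". No threshold, random term or mixed-model formula follows.

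**Unit of assignment.** The Protocol's opening paragraph says "A multi-site within-school randomized control trial (RCT) intervention design was employed" and does not say whether pupils or classes were randomised. Aims 2 and 3 call the intervention class-based. Under Procedure and Scenarios, the weekly session ends with a teacher-led discussion: "Teachers ask the students to sit in a circle on the floor in the front of the classroom for the discussion".

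**The concern.** The issue is the form in which classroom enters the model. A class that receives the program together belongs to one arm, one grade and one school. If assignment was by class, a full set of classroom dummies already accounts for every difference between arms and between grades. Nothing is left from which to estimate a treatment effect or a treatment-by-grade effect.

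The software still returns a number. `lm` shows NA for the terms it drops but prints a treatment coefficient with a p-value. `polr` drops terms with a warning. `multinom` returns one of many equivalent solutions without a warning. A contrast of arbitrary classrooms could therefore be read as the program effect, and hypothesis 1.3 (effects varying by grade) would have no estimate. AIC favours this model when classroom variation is material, which is when proper handling of classroom matters most.

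**Working it through.** The documents give no power, ICC or class-count figure, so there is no plan figure to reproduce. The check covers identifiability first, then size.

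**Inputs.** From the documents: N = 885, three grades, significance at .05, and the three model formulas. Assumed: 42 classes of about 21 (885/42 = 21.1), assigned 1:1 by class within grade; pretest slope 0.5; outcome SD about 1; classroom ICC 0.05, with other values where noted.

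**1. Rank, with K classes.** Columns are intercept 1, pretest 1, treatment 1, grade 2, treatment-by-grade 2 and classroom K − 1, giving K + 6. The independent directions are K class means plus the pretest, giving K + 1. The deficiency is (K + 6) − (K + 1) = 5 for any K. For 30, 42 and 60 classes: 36 columns against rank 31, 48 against 43, and 66 against 61. Without the interaction there are K + 4 columns, so the deficiency is 3. Race/ethnicity varies within class and does not alter this. The result does not depend on ICC or effect size.

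**2. What R returns (simulated data, 42 classes).**
- `lm` set the last three classroom dummies and both treatment-by-grade terms to NA. The treatment coefficient was −0.0430, exactly the adjusted mean of class 40 minus that of class 1. Changing only the reference class moved it between −0.076 and +0.527 on the same data. Entering classroom before treatment made treatment NA.
- `polr` warned of rank deficiency and dropped terms. Its treatment coefficient moved from 0.12 to 0.63 when the reference class changed.
- `multinom` gave no warning. Its two treatment coefficients moved from −0.12 and −0.43 to −0.22 and +0.64.
- A random-intercept fit to the data used for `lm` gave a single estimate, 0.113 (SE 0.087).

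Because `lm` drops both interaction columns anyway, its fits with and without the interaction are the same model.

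**3. Precision at ICC 0.05.** Let b be the between-class variance, w the within-class residual variance, and m = 21. Two readings of the ICC are used: a share of residual variance (b = 0.05, w = 0.95), or a share of total variance with the pretest explaining 0.25 (b = 0.05, w = 0.70).

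| Quantity | Formula | Residual ICC | Total ICC |
|---|---|---|---|
| SD, two-class contrast | √[2(b + w/m)] | 0.436 | 0.408 |
| SE the model reports | √(2w/m) | 0.301 | 0.258 |
| False positives | P(\|Z\| > 1.96 × SE/SD) | 17.7% | 21.5% |
| SD using all 42 classes | √[(2/21)(b + w/m)] | 0.095 | 0.089 |
| Child-level OLS: design effect | 1 + 20b/(b + w) | 2.00 | 2.33 |
| Child-level OLS: false positives | P(\|Z\| > 1.96/√design effect) | 16.6% | 19.9% |

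Simulations of 300 to 400 trials per setting agree. The dummy model gave SD 0.40–0.435 and false positives of 15.5–23%. Without dummies the SD was 0.08–0.09. Child-level OLS rejected a true null in 13–20% of trials. Under the total-variance reading, a true effect of 0.20 has the wrong sign with probability Φ(−0.20/0.408) = 31%, as simulated.

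**4. How often the dummies are chosen.** They add 42 − 4 = 38 estimable parameters to the no-interaction model. AIC needs a deviance drop above 2 × 38 = 76. BIC needs 38 × ln 885 = 257.9. The expected drop is roughly 885 × ln[1 + 38F/842] with F = (w + 21b)/w, where 842 = 885 − 43. Residual ICC gives F = 2.11 and a drop of 80.3. Total ICC gives F = 2.50 and a drop of 94.6. Both pass the AIC threshold and fall far short of BIC's. In simulation AIC chose the dummies in about 55% (residual) and 80% (total) of trials, and BIC in about 0%. With residual ICC, AIC chose them in about 3–7% of trials at 0.02 and 95–98% at 0.10, and BIC never did.

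**The case against.** - **The premise is not in the documents.** The unit of assignment is nowhere stated. If pupils were randomised within classes, classroom dummies would be harmless. This stands, and the point is conditional on it. A weekly whole-class discussion led by the teacher makes pupil-level assignment hard to picture but does not rule it out.
- **The rule names BIC as well as AIC.** If both must agree, the aliased model would almost never be chosen at ICC 0.10 or below. This also stands. The SAP gives no rule for a conflict, however, and the two criteria conflict over the range where classroom variation matters.
- **Multilevel modelling is mentioned.** A random classroom effect is therefore not excluded, and it would be wrong to call a fixed effect the only route. But no trigger or formula is given, and the only specified form for classroom is fixed.
- **The problem would be noticed.** `polr` warns, and `lm` shows NA for both treatment-by-grade terms, so the dropping is not silent. This lowers the chance of misreporting, but the printed treatment coefficient still looks ordinary and `multinom` gives no sign.
- **The number of outcomes affected is not fixed.** The base models cover five composites, five sets of ordinal items and one multinomial outcome. Factor analyses may turn three of the ordinal sets into composites. The SAP's list of measures subject to model selection also names school but not classroom, although a later sentence includes it.

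**Conclusion.** The concern holds in conditional form. If whole classes were assigned, any model with classroom dummies cannot estimate the treatment effect or test hypothesis 1.3. That part is algebra. Treatment-by-gender and treatment-by-race terms can still be estimated from within-class variation. For `multinom`, the result is best described as an arbitrary, non-unique solution rather than a contrast of particular classrooms.

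The sizes (SD about 0.4 against 0.08–0.09; false positives about 15–23%) rest on assumed class count, ICC and pretest slope, and apply only once the dummy model has been chosen. A reader might take them as error rates of the SAP's whole procedure, or conclude that reported results are contrasts of arbitrary classrooms. The documents support neither: they do not state the unit, show which model was selected for any outcome, or say whether multilevel models were used. Omitting classroom is not a safe fallback, since child-level OLS also rejects too often.

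**What to change.** 1. State the unit of assignment in the Protocol and SAP.
2. If it is the class, remove classroom from the candidate fixed effects and account for it in every model, whatever AIC and BIC show. Use a random intercept in a linear mixed model for composites and in a cumulative-link mixed model for ordinal items. For occupation expectations, use a mixed logit or classroom-clustered standard errors.
3. Keep school and grade as fixed effects.
4. State that no fit with an aliased or dropped treatment or treatment-by-grade term is reported.
5. The SAP is written in the past tense, so check which outcomes were analysed with classroom dummies and rerun them.

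If pupils were randomised within classes, stating so resolves this point.

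The cost is a few lines of SAP text, somewhat more analysis work across the 30 imputed datasets, and wider intervals than a child-level model gives.
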